Neck static stretching acutely reduces blood pressure through reduction of tissue stiffness: A randomized crossover trial

NCT Number: NCT07197047

Document Date: 07/10/2025

Study Protocol

This study hypothesised that static stretching (SS) of the right posterolateral cervical region would elicit a reduction in blood pressure (BP), potentially mediated by specific physiological mechanisms. Accordingly, the aim of this study was to investigate the acute effects of SS of the posterolateral neck region on BP and to explore the potential moderating roles of tissue hardness (TH) and heart rate variability (HRV). Twenty-five healthy participants were enrolled in a randomised crossover design. Each participant completed two experimental conditions: a SS session (SS) and a control condition (CC). The order of conditions was randomly determined using the website www.randomizer.org. During each visit, measurements were obtained at two time points: baseline (T0, upon arrival) and immediately after the assigned condition (T1). At each assessment point, outcomes were collected in a standardised sequence: BP was measured first, followed by bilateral assessments of TH adjacent to the seventh cervical vertebra (C7), and subsequently by recordings of HRV and heart rate (HR). Between T0 and T1, participants either performed the static stretching protocol (SS) or completed a 6-minute seated rest period (CC), with the duration of the control period matched to that of the stretching intervention.

Statistical Analysis Plan (SAP)

Data will be expressed as means \pm standard deviations. Baseline comparisons between conditions (SS vs. CC) will be assessed using paired *t*-tests for all variables. To evaluate the effects of time (T0 Vs. T1) and condition (SS Vs. CC), a repeated-measures ANOVA (2×2 design) will be performed. When significant time \times condition interactions are identified, post hoc analyses with Scheffé adjustments will be conducted to determine specific within- and between-condition differences. Effect sizes (ES) will be calculated for all primary analyses, with partial eta squared (η^2_p) used as the index of ES. The magnitude of effects will be interpreted as small (0.01–0.059), moderate (0.06–0.139), or large (≥ 0.14). All statistical analyses will be performed using Jamovi software (version 2.6.13.0; The Jamovi Project, 2025; <https://www.jamovi.org>), with statistical significance set at $p < 0.05$.

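### No planned analysis relates tissue hardness or heart rate variability to blood pressure, so the exploratory aim cannot be answered and the title's mechanism claim lacks support

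*Combined protocol and SAP*

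**What the plan says.** Three statements about mechanism appear in the document, and they do not match.

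- **Title:** "Neck static stretching acutely reduces blood pressure through reduction of tissue stiffness: A randomized crossover trial". This is a mediation claim, stated without a hedge.
- **Study Protocol, hypothesis:** stretching "would elicit a reduction in blood pressure (BP), potentially mediated by specific physiological mechanisms". This is mediation, hedged.
- **Study Protocol, aim:** "to explore the potential moderating roles of tissue hardness (TH) and heart rate variability (HRV"). This is moderation, exploratory.

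The SAP then gives three analyses.

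- **Baseline:** "Baseline comparisons between conditions (SS vs. CC) will be assessed using paired" t-tests.
- **Main:** "a repeated-measures ANOVA (2×2 design) will be performed", with time (T0, T1) and condition (stretching, SS; control, CC) as the factors.
- **Follow-up:** Scheffé-adjusted contrasts within and between conditions when the interaction is significant.

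Partial eta squared is the effect-size index. The SAP names no covariate, moderator term, correlation, regression or mediation model.

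On data collection, the Study Protocol states: "During each visit, measurements were obtained at two time points: baseline (T0, upon arrival) and immediately after the assigned condition (T1"). Within each time point, "BP was measured first, followed by bilateral assessments of TH adjacent to the seventh cervical vertebra (C7"), and HRV comes last.

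**The concern.** Mediation and moderation are different questions. Mediation asks whether the change in TH or HRV accounts for the change in BP. Moderation asks whether a participant's level of TH or HRV alters the size of the BP response. *Moderating* may be a slip for *mediating*, but the plan does not say, and each needs its own model.

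Neither model is in the SAP. The SAP does not name the outcomes for the ANOVA; the natural reading is one ANOVA per outcome. On that reading each analysis handles one variable at a time. It can show whether BP changed and whether TH changed, but not whether the two changes are linked.

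Two things are at stake. A plan followed exactly cannot answer the second part of its own aim. And two significant interactions could be reported as evidence for the title's mechanism when they are compatible with unrelated changes.

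**Working it through.** The documents give no power, effect size or SD, so there is no planned figure to reproduce. The only inputs taken from them are n = 25, the crossover design and the 0.05 level. A two-sided test is assumed. All effect sizes *d* and correlations *r* below are assumptions for illustration.

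**1. What the ANOVA can see.** For each participant take D = (T1 − T0 under SS) − (T1 − T0 under CC). In a 2×2 within-subject ANOVA the time × condition F equals t², where t = mean(D) / (SD(D)/√25). F for BP depends only on D(BP), and F for TH only on D(TH). How the two sets of values pair up across participants does not enter.

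A simulated data set shows this. Shuffling the TH values among participants left both F values unchanged (BP 20.94, TH 19.38), while the correlation between the BP and TH changes fell from 0.80 to 0.13.

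**2. How often both interactions are significant when the changes are unrelated.** With independent changes and the same *d* for both outcomes, the probability is the square of the single-test power (noncentral t, 24 df, noncentrality d√25 = 5d).

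| d | Power, one interaction | Both significant |
|---|---|---|
| 0.3 | 0.302 | 0.302² = 0.09 |
| 0.5 | 0.670 | 0.670² = 0.45 |
| 0.8 | 0.970 | 0.970² = 0.94 |

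In 20,000 simulated trials per scenario at d = 0.8, both were significant in 94.1% when the true correlation of changes was 0 and in 95.7% when it was 0.9. The planned output is almost the same in the two cases.

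**3. What an added analysis could deliver.** Use Fisher's z with k covariates, SE = 1/√(22 − k). The 80% power multiplier is 1.96 + 0.84 = 2.80.

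| | Mediation model, k = 2 | Moderation model, k = 1 |
|---|---|---|
| Detectable partial \|r\| at 80% power | tanh(2.80/√20) = 0.556 | tanh(2.80/√21) = 0.545 |
| 95% CI if observed r = 0.4 | tanh(0.424 ± 0.438) = −0.015 to 0.697 | tanh(0.424 ± 0.428) = −0.004 to 0.692 |
| 95% CI if observed r = 0 | ±0.412 | ±0.403 |

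Direct simulation of the mediation slope (21 residual df) gives 49% power at r = 0.4, 71% at 0.5 and 83% at 0.56.

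**4. Indirect effect.** This is the mean of D(TH) times the slope, with a percentile-bootstrap CI. The simulations took the average TH change as independent of the other terms and split condition order 13/12. The ranges cover repeated runs.

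| TH effect d | CI excludes zero, r = 0.56 | CI excludes zero, r = 0.4 |
|---|---|---|
| 0.5 | 55–57% | 33–36% |
| 0.6 | 66–70% | 39–41% |
| 0.8 | 77–81% | 48–49% |

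**The case against.** The strongest reply is that both the aim and the hypothesis are hedged, the BP comparison is intact, and the proposed regression is weak at 25 participants. On that view only a causal word in the title and a mismatch of terms remain. Most of this stands: it limits the severity and makes rewording a full remedy. It does not remove the point, because exploring an aim still needs an analysis and the title carries no hedge.

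A second reply is that separate ANOVAs do test the mechanism, since TH must change if it is to mediate. That is a necessary step and it is not sufficient. It is also a soft test in the other direction: a non-significant TH interaction would be only weak evidence against the mechanism, because power for one interaction is about 30% at d = 0.3 and 67% at d = 0.5.

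Three criticisms of the added models are fair and belong among their limits.

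- The mediation slope uses only differences between participants in TH response. If TH fell by a similar amount in everyone, the regression would be uninformative even if the mechanism were real. Measurement error in TH would also weaken the slope.
- For participants who stretched first, the second-visit T0 value comes after treatment, and the document states no washout interval. The order covariate absorbs a uniform shift, but not carryover that differs between participants.
- The BP measure has to be named, or an outcome choice is left open.

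**Conclusion.** The concern holds and should be fixed. None of the three planned analyses relates TH or HRV to BP. The exploratory aim therefore cannot be answered as written, and the planned results would be insufficient to support *through*.

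This conclusion is structural. It rests on reading the SAP as one ANOVA per outcome and not on any assumed effect size; the percentages above only illustrate it. The BP aim is unaffected, because the time × condition interaction addresses it. An added analysis would also have limited reach: a null result would exclude only a strong association.

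**What to change.** State whether mediation or moderation is meant, and make the title, hypothesis and aim agree. Then take one of these routes.

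- **Mediation.** Regress each participant's SS − CC difference in change of a named BP measure on the SS − CC difference in TH change, with the side named. Covariates are the mean-centred average TH change over the two conditions and centred condition order, which is available because "The order of conditions was randomly determined using the website www.randomizer.org". Report the indirect effect with a bootstrap 95% CI. Fit a separate model for one named HRV index.
- **Moderation.** Regress the same BP difference on mean-centred T0 TH (or HRV) averaged over the two visits, with condition order as a covariate. State the assumption of no carryover into the second-visit T0 values.
- **Wording only.** Describe parallel BP, TH and HRV responses, remove the mediation and moderation language, and drop *through* from the title.

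Label any added analysis exploratory, and post hoc if it is added after the data were seen. State its limits: BP was recorded before TH and HRV at each time point, TH was not itself randomised, a mediation slope depends on between-participant variation in response, and precision at 25 participants is low.

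The cost is one short regression per candidate variable on measurements already taken, or a change of wording. The downside is a softer mechanism claim, or one estimated imprecisely and possibly post hoc.

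### Blood pressure at T0 is taken on arrival with no prior rest described: arrival noise reduces precision, and settling enters the time effect and the size of any within-stretching fall

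*Combined protocol and SAP*

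**What the plan says.** The Study Protocol sets two time points per visit. The first is "baseline (T0, upon arrival"); the second, T1, comes directly after the condition. At each of them "BP was measured first, followed by bilateral assessments of TH adjacent to the seventh cervical vertebra (C7"), and HRV and heart rate are recorded last. T0 BP is therefore the reading closest to arrival. No seated rest, acclimatisation or repeat reading before it is described.

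In the stretching visit, the stretching takes place between T0 and T1. In the control visit, participants instead "completed a 6-minute seated rest period (CC), with the duration of the control period matched to that of the stretching intervention". Posture during stretching is not stated.

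The SAP plans a 2×2 repeated-measures ANOVA: "To evaluate the effects of time (T0 Vs. T1) and condition (SS Vs. CC"). If the interaction is significant, Scheffé-adjusted post hoc tests follow, "to determine specific within- and between-condition differences". T0 values are compared between conditions by paired t-tests. No adjustment for T0 is described, and the interaction is not named as the sole test of the BP hypothesis.

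**The concern.** A reading taken on arrival carries the after-effects of getting to the visit, and part of these will have faded by T1. The T0–T1 change then mixes the effect of the condition with settling. The control condition, quiet sitting, is the activity in which settling would be expected.

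Three things are at stake:

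- **Precision.** Arrival state differs between a participant's two visits, and that difference passes into the SS−CC difference in change, which is the comparison that answers the question.
- **Interpretation.** The time main effect is tested whatever the interaction shows, and settling does not cancel in it. Nor does it cancel in the size of a within-stretching fall.
- **Bias.** If BP settles by different amounts during sitting and stretching, the interaction absorbs the gap.

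**Working it through.** **Inputs from the documents:** n = 25, two-condition crossover, two time points per visit, significance at p < 0.05 (two-sided assumed). The documents give no SD, effect size, power or settling figure, so there is no plan figure to reproduce. Every mmHg input below is an assumption.

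**What cancels.** With two conditions and two time points, the interaction test is a paired t-test on D = (T1−T0 under SS) − (T1−T0 under CC), with 24 degrees of freedom. If mean settling is M in both conditions, D contains M − M = 0. A simulation with equal settling and no stretching effect rejected the interaction in 5% of runs, as it should.

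**(a) Precision.** Assume that the SD of D is 7 mmHg without arrival variation, that arrival state has visit-level SD τ at T0, and that 30% of it persists at T1. Each visit's change then carries 0.7τ, and

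SD(D) = √(7² + 2(0.7τ)²).

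For n = 25 the difference detectable with 80% power is 0.584 × SD(D) (non-central t).

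| τ (mmHg) | SD(D) | Detectable difference | Power for 4 mmHg |
|---|---|---|---|
| 0 | 7.0 | 4.1 | 78% |
| 3 | √(49 + 8.8) = 7.6 | 4.4 | 71% |
| 5 | √(49 + 24.5) = 8.6 | 5.0 | 61% |
| 7 | √(49 + 48.0) = 9.8 | 5.8 | 50% |

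The pattern does not hinge on the 7. With a starting SD of 6 and settling SD per visit of 0, 2, 4 and 6 entering in full, SD = √(6² + 2·SD²settling), the detectable difference is 3.5, 3.9, 4.8 and 6.1 mmHg.

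**(b) Time main effect.** Assume settling of 3 mmHg in both conditions, no stretching effect, and SD of a single change s. The test uses each participant's mean of two changes, with SD s√((1+ρ)/2), where ρ is the correlation of changes between visits.

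| s (mmHg) | Significant, ρ = 0 | Significant, ρ = 0.5 |
|---|---|---|
| 5 | 98% | 91% |
| 6 | 92% | 79% |
| 8 | 72% | 55% |

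**Within-stretching fall.** In the same scenario with ρ = 0, the interaction is significant in about 5% of trials. A significant interaction together with a significant within-SS fall occurs in about 2.5–3%, before the Scheffé adjustment. The gate controls how often a fall is declared. It does not correct its size: expected within-SS change = stretching effect + settling.

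**(c) Unequal settling.** If settling during stretching is a fraction f of that during seated rest, bias in D = (1 − f) × settling over the six minutes. If all 3 mmHg fell in that interval, f = 0.75 or 0.50 would give 0.75 or 1.5 mmHg. With SD(D) = 7, power for a true 4 mmHg effect would fall from 78% to 61% or 40%. These are ceilings, because some settling happens during the tissue-hardness and HRV/heart-rate recordings that follow T0 BP in both conditions, and that part is common.

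**The case against.** The strongest reply is that the design already deals with this. A randomised crossover with a duration-matched seated control removes settling that is common to both conditions, and both conditions pass through the same recordings after T0 BP before they diverge. That stands, and it is why the point does not undermine the interaction as such.

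A reader might infer that the plan would often declare a false within-stretching fall, since an unadjusted T0–T1 test would be significant in 67% of trials (44–82%) with 3 mmHg settling and a change SD of 6 (8–5). The documents do not support that: those tests are run only after a significant interaction, and with Scheffé adjustment.

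A reader might also infer that unequal settling could manufacture a BP-lowering result. No figure in the documents shows unequal settling. If stretching slows settling, the bias runs against the hypothesis. The direction cannot be fixed from the text.

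The time main effect is not presented as evidence for stretching, and the SAP uses the interaction to trigger further testing. That is fair, but the SAP does not say that the BP conclusion rests on the interaction alone.

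The protocol is one paragraph and gives little BP procedure, so a rest may have been used and not described. It is also written in the past tense, so a change in T0 timing may come too late.

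**Conclusion.** The point holds as a matter of precision and interpretation, and does not invalidate the trial. Followed as written, the T0 rule adds arrival noise to the deciding contrast, at a cost of roughly 0.4 to 1.7 mmHg in detectable difference (4.1 to 4.4–5.8) under the assumptions in (a). Those figures are an upper bound on what a rest before T0 would recover, because they compare against no arrival variation at all. The time main effect cannot be read as an effect of stretching, and a within-stretching fall is inflated by whatever settling occurred. Bias in the interaction is conditional on unequal settling and cannot be sized from the documents. It merits a change, with medium confidence, since the size rests wholly on assumed mmHg values.

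**What to change.** **Protocol, for any visits still to be done (or a repeat trial):** replace measurement on arrival with T0 taken after a fixed seated rest, of the same length and posture at both visits. The six minutes already used in the control would serve. If such a rest was in fact used, say so.

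**SAP, also for data already collected:** state that the BP conclusion rests only on the time × condition interaction, reported as the SS−CC difference in change with a 95% CI. State that the time main effect and the within-condition T0–T1 changes are descriptive and not evidence that stretching lowers BP.

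**Cost:** a few more minutes per visit, with no extra staff or equipment, and two sentences in the SAP. The within-stretching fall will look less striking. The SAP change corrects interpretation only; it does not restore precision lost in data already collected.

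### Optional improvement: the planned 2×2 ANOVA leaves out the randomised order of conditions; a sequence-adjusted change estimate would cost one degree of freedom

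*Combined protocol and SAP*

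**What the plan says.** The Study Protocol section describes a two-visit crossover: "Twenty-five healthy participants were enrolled in a randomised crossover design". On order it says only this: "The order of conditions was randomly determined using the website www.randomizer.org". It does not give the number allocated to each order, any restriction on the randomisation, or the interval between visits. T0 and T1 are measured at both visits.

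The Statistical Analysis Plan names two factors: "To evaluate the effects of time (T0 Vs. T1) and condition (SS Vs. CC), a repeated-measures ANOVA (2×2 design) will be performed". A significant time × condition interaction leads to Scheffé-adjusted comparisons, and partial eta squared is the effect size. T0 otherwise appears in one place: "Baseline comparisons between conditions (SS vs. CC) will be assessed using paired *t*-tests for all variables". No sequence term, period term or T0 covariate is mentioned.

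**The concern.** In a two-period crossover, each participant's SS−CC contrast is also a visit 1 versus visit 2 contrast, in a direction set by the order. Suppose the T0-to-T1 change tends to differ between a first and a second visit, for example because participants are more at ease the second time. A model without order cannot separate that from the stretching effect within a given split. Two consequences would follow. The period difference inflates the residual, so the error bars are wrong. If more participants took one order than the other, part of the period difference also enters the estimate. With 25 participants the split cannot be exactly even, and the SAP does not ask for it to be reported.

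**Working it through.** **Inputs.** From the documents: N = 25, two conditions in random order, T0 and T1 at each visit, significance at p < 0.05. The documents give no SD, effect size, period effect, order split or power calculation, so there is no planned figure to reproduce. Assumed: SD of the SS−CC change difference 8 mmHg; period effect π = 4 mmHg, meaning that the T0-to-T1 change is 4 mmHg larger at visit 1 than at visit 2; approximate normality. The percentages depend only on π/SD = 0.5.

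**Step 1: what the planned test is.** For each participant let D = (T1−T0) under SS minus (T1−T0) under CC. The 2×2 interaction F(1,24) is the square of the one-sample t on D. On a test data set both came to 10.1749. A visit-to-visit shift in level that is common to T0 and T1 cancels in D. A visit-to-visit difference in the change does not.

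**Step 2: shift and error bars given the split.** D has mean τ + π in SS-first participants (n1) and τ − π in CC-first participants (n2). So:
- Shift of the planned estimate = π × (n1−n2)/25.
- True SE = 8/√25 = 1.60.
- Expected residual variance used by the plan = 64 + 16 × [1 − ((n1−n2)/25)²] × 25/24.
- Sequence-adjusted SE = (8/2) × √(1/n1 + 1/n2), with no shift.

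| Split | Shift (mmHg) | Plan's residual variance | Plan's SE (√variance/5) | Sequence-adjusted SE |
|---|---|---|---|---|
| 13/12 | 4 × 1/25 = 0.16 | 80.64 | 1.80 | 1.601 |
| 15/10 | 4 × 5/25 = 0.80 | 80.00 | 1.79 | 1.633 |
| 17/8 | 4 × 9/25 = 1.44 | 78.51 | 1.77 | 1.715 |

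**Step 3: type I error.** Simulation under no stretching effect gives about 3% (13/12), 5% (15/10) and 10% (17/8) for the planned test. It gives 5% for the sequence-adjusted fit at every split. Averaged over unrestricted random order, the planned test has 5.1%. At 13/12 the planned test is conservative. Its mean CI width is 0.917 SD against 0.818 SD with sequence, which is 0.917 × 8 = 7.3 against 0.818 × 8 = 6.5 mmHg.

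**Step 4: how likely an uneven split is.** If randomisation was unrestricted, which the documents neither state nor exclude, Binomial(25, 0.5) gives 42% for 15/10 or worse and 11% for 17/8 or worse.

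**Step 5: cost if there is no period effect.** The critical t moves from 2.0639 (24 df) to 2.0687 (23 df), a ratio of 1.0023. The CI width ratio is (sequence-adjusted SE/1.60) × 1.0023:
- 13/12: 1.0008 × 1.0023 = 1.003
- 15/10: 1.0206 × 1.0023 = 1.023
- 17/8: 1.0719 × 1.0023 = 1.074

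Averaged over unrestricted randomisation, with an assumed 4.5 mmHg effect, power goes from 77% to 75% with no period effect. It is 75% either way at 2 mmHg, and goes from 68% to 75% at 4 mmHg.

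**Step 6: using T0 as a covariate.** The plan uses T0 by subtraction, a slope fixed at 1. Let ρ be the correlation between the SS−CC differences at T0 and T1, with equal variances assumed. Estimating the slope as well as sequence narrows the CI by about 9% at ρ = 0.5 and 0.4% at ρ = 0.8, and widens it by 2% at ρ = 0.9. Now let a carryover λ after SS shift visit-2 T0 and T1 equally. The change estimate, once adjusted for sequence, is unaffected. The T0-adjusted intercept is biased by (1−slope) × λ/2 in size. At λ = 4 and slope 0.5 this is 0.5 × 4/2 = 1.0 mmHg, with type I error of about 10%.

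**The case against.** The strongest reply is that nothing here is broken, and that stands. Order was randomised, so the planned estimate is unbiased over random order and its overall type I error is about 5%. The 10% figure needs both a 17/8 split and a 4 mmHg period effect, and the documents support neither. At the split nearest to even the planned test errs on the safe side. Adding sequence also gives up a little power unless the period effect exceeds about 2 mmHg (0.25 SD).

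A reader might infer three stronger points, and the documents support none of them.
- *The planned ANOVA is biased or invalid.* It is not; the shift arises only given an uneven split and a period effect in the change.
- *The T0-adjusted model should replace the planned contrast because it is more precise.* Its gain depends on ρ, which is not given, and is essentially gone at ρ of 0.8 to 0.9. No interval between visits is stated, so carryover into visit-2 T0 cannot be ruled out. The change estimate is not safe everywhere either: if a 4 mmHg carryover is halved by T1 (ρ = 0.5), it is biased by 1.0 mmHg and the T0-adjusted one by 0. This is a trade-off. The planned baseline t-test cannot settle it, since it would be significant in only 21% (ρ = 0.5) or 15% (ρ = 0.7) of trials with a 4 mmHg level carryover.
- *The unstated interval shows that carryover occurred.* It is a missing detail and shows nothing either way. The sequence term neither tests for carryover nor removes it.

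It is also fair to say that prespecification may no longer be possible. The protocol says that participants were enrolled and completed both conditions, and the document title already states a result.

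**Conclusion.** Optional improvement. The planned interaction test ignores the randomised order. It is valid on average but, given the split that occurred, can be too conservative or too liberal if the T0-to-T1 change differs between visits. At an assumed period effect of half an SD, its type I error ranges from about 3% to 10% across splits from 13/12 to 17/8, where the sequence-adjusted fit stays at 5%. The SD, period effect and splits are all assumptions. The percentages carry over to tissue hardness, HRV and heart rate only as far as their change differences are roughly normal, which was not checked. The case for acting is that the data are already collected and the cost is small at a near-even split.

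**What to change.** 1. For each outcome, regress the SS−CC difference in T0-to-T1 change on sequence, coded +1/−1. Report the intercept with a 95% CI as the main stretching effect.
2. Report the number of participants in each order.
3. As a labelled sensitivity analysis only, regress the SS−CC difference at T1 on sequence and on the uncentred SS−CC difference at T0. Say that carryover which shifts visit-2 T0 and T1 equally can bias it.
4. Date the change relative to the analysis and report the planned ANOVA beside the new estimate. If outcome data have been seen, label the sequence-adjusted estimate a sensitivity analysis too.
5. State which analysis triggers the Scheffé comparisons and supplies partial eta squared. Both can stay with the planned ANOVA.

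Cost: no new data and 1 of the 24 error degrees of freedom. With no period effect the CI is about 0.3% wider at 13/12, 2.3% at 15/10 and 7.4% at 17/8.

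### The Scheffé family is not stated: over the four cell means it is valid but stricter than four simple comparisons need; Holm over those four serves better

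*Combined protocol and SAP*

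**What the plan says.** The main analysis in the SAP is stated as follows: "To evaluate the effects of time (T0 Vs. T1) and condition (SS Vs. CC), a repeated-measures ANOVA (2×2 design) will be performed". After a significant time × condition interaction, it turns to Scheffé: "condition interactions are identified, post hoc analyses with Scheffé adjustments will be conducted to determine specific within- and between-condition differences". The overall significance level is 0.05.

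Three related statements matter here.

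- The Study Protocol gives the sample: "Twenty-five healthy participants were enrolled in a randomised crossover design", and "Each participant completed two experimental conditions". With 25 complete pairs, any paired contrast has 24 error df.
- The SAP also plans a separate baseline test: "Baseline comparisons between conditions (SS vs. CC) will be assessed using paired" t-tests, for all variables, with no adjustment mentioned.
- The only effect measure named is partial eta squared: "Effect sizes (ES) will be calculated for all primary analyses, with partial eta squared".

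The SAP does not say how many comparisons the Scheffé family contains, whether it covers the four cell means or each two-level factor separately, or which error term is used. It plans no complex contrast and gives no reason for choosing Scheffé.

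**The concern.** Scheffé protects every conceivable contrast among a set of means. That is worth paying for when contrasts are chosen after seeing the data. Here the within- and between-condition differences in a 2×2 layout come to four simple comparisons: T0 versus T1 within SS, T0 versus T1 within CC, SS versus CC at T0, and SS versus CC at T1. The count of four is inferred from the layout; the SAP does not give it.

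If the family is the four cell means, the plan pays for protection it does not use. After a significant interaction, Scheffé may then leave SS versus CC at T1 non-significant where an equally valid procedure would flag it. What is at stake is locating the difference, not detecting the stretch effect, because the 1-df interaction test carries no Scheffé adjustment.

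**Working it through.** The plan gives no critical value or power figure, so there is nothing of its own to reproduce.

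**Inputs.** From the documents: n = 25, alpha 0.05 (taken as two-sided), 2 × 2 = 4 cell means. Assumed: contrast-specific (paired) error on 24 df, and Scheffé over the four cell means. The four simple comparisons have rank 3, so the multiplier is 3 even if only those four are considered.

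**Thresholds on 24 df**

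- Scheffé: sqrt(3 × F0.95(3, 24)) = sqrt(3 × 3.009) = 3.004, a per-comparison p of 0.0061.
- Bonferroni over all six pairs: 2.875.
- Holm over four, in turn: 2.700, 2.574, 2.391, 2.064.

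**Validity.** The Bonferroni bound on familywise error for the four under Scheffé is 4 × 0.00614 = 0.0246, below 0.05.

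**Dominance.** Scheffé requires p below 0.0061, and Holm's strictest step is 0.05/4 = 0.0125. On the same t statistics, Holm therefore rejects whatever Scheffé rejects, whatever the variances. With pooled error on 72 df the order is the same (2.863 against 2.562). The general-covariance form is stricter still: sqrt(3 × 24/22 × F0.95(3, 22)) = 3.159.

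**The other reading.** Within a two-level factor the Scheffé rank is 1 and the threshold is 2.064, which is no adjustment. With all four nulls true and no interaction gate, the chance of any false rejection is about 16–17%. The gate, itself a 5% test, caps that particular case at 5%. It gives no such cap once a real stretch effect opens it.

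**Size of the loss.** The documents give no variance components, so the ratio of visit variance to error variance is an assumption, shown as a range. The simulation used 800,000 trials per ratio, error SD 1, and no change in CC. The SS effect at T1 was 2 × 0.584 = 1.168, which gives the interaction 80% power. Percentage of trials flagging SS versus CC at T1, given a significant interaction:

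| Visit/error variance ratio | Scheffé | Holm over six pairs* | Holm over four | Unadjusted |
|---|---|---|---|---|
| 0 | 93.0 | 96.3 | 97.6 | 99.6 |
| 1 | 54.6 | 64.0 | 70.3 | 85.6 |
| 2 | 33.7 | 42.1 | 49.2 | 68.4 |
| 4 | 17.1 | 22.9 | 28.6 | 46.6 |

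*200,000 trials per ratio.

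The within-SS change is flagged in 93% (Scheffé) against 97–98% (Holm over four) at every ratio. No planned comparison was rejected by Scheffé and missed by Holm in 3.2 million trials. At ratio 1 the gain is 70.3 − 54.6 = 15.7 points. Of this, 64.0 − 54.6 = 9.4 points come from the method and 70.3 − 64.0 = 6.3 from leaving out the two cross-diagonal pairs.

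**Error rates**

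- All four null, no gate: Scheffé 2.2–2.3%, Holm 4.4–4.7%.
- Stretch effect present, given a significant interaction, any false rejection among the two true nulls: about 0.9% with Scheffé, about 3.3% with Holm.

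**The T0 overlap.** The baseline paired t-test is the same hypothesis and the same t on 24 df as SS versus CC at T0. If it also stays as an unadjusted inferential test, familywise error over the four with Holm is about 7.6–7.9% when all are null, and about 6% with the interaction gate. The 5% claim then fails. The overlap already exists under Scheffé: 6.3–6.5%, or 5.7% with the gate.

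**The case against.** The strongest reply is that the premise is not in the SAP. No family, rank or error term is given, and the software version that it names may settle both in a way that the documents do not reveal. A reader might infer that the planned post hoc tests simply are too conservative. The documents do not support that unconditionally, because at rank 1 the problem reverses to no adjustment at all. This part stands, and it is why the conclusion is conditional. It does not remove the point, since the same remedy serves under either reading.

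Two other strong readings should be resisted. One is that Scheffé endangers the trial's main finding. It does not: the interaction test is untouched, and on these simulations the within-SS change is still flagged in 93% of trials with a significant interaction. The other is that the low T1 rates are Scheffé's doing. Much of the shortfall is visit variance: at ratio 4 even the unadjusted test reaches only 47%.

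It is also fair to say that choosing a stricter valid method is not an error, that Scheffé offers matching simultaneous intervals which Holm does not readily give, and that Holm raises the false-rejection rate while staying below 5%. All of that stands and keeps the point minor.

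Finally, the protocol's past tense and the document's title might suggest that the results are already known. The SAP is written in the future tense, so the documents do not settle whether the data have been analysed.

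**Conclusion.** The point holds in conditional form, as a low-cost improvement and not a flaw that threatens validity. If Scheffé is applied over the four cell means, Holm over the four simple comparisons rejects everything Scheffé does at the 0.05 level. It also holds 5% familywise error, provided T0 is tested only once. If Scheffé is applied within each factor, the comparisons are unadjusted and Holm supplies the missing control.

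The comparison of thresholds needs only n = 25, the rank-3 reading and the same t statistics in both methods. A pooled-error Scheffé can occasionally reject where Holm on paired tests does not, because the error terms differ. The gain at T1 rests further on the assumed variance ratios, 80% interaction power and no change in CC: about 5 points at ratio 0 (97.6 − 93.0) and 11 to 16 points at ratios 1 to 4. The within-SS gain is 4 to 5 points.

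**What to change.** Amend the SAP as follows.

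1. After a significant interaction, use Holm over the four simple comparisons, separately for each outcome, with paired error on 24 df. State the family and the error term.
2. Test T0 inferentially once only. Either report the baseline paired t-test as descriptive and take T0 inference from the Holm family, or leave T0 to the baseline test, use Holm over the other three, and claim 5% control for those three only.
3. Report the interaction as the SS-minus-CC difference in T0–T1 change with its 95% CI. Partial eta squared gives neither the direction nor the units of the effect.

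The cost is a few SAP sentences and no new data. What is given up is protection for complex and cross-diagonal contrasts (none is planned), ready simultaneous intervals, and some of the unused error margin: about 0.9% rising to about 3.3% given a significant interaction with the stretch effect present. Control is within each outcome; the change does nothing about multiplicity across outcomes.

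Document the switch before the data are analysed. If they already have been, keep Scheffé as planned, state how it was applied, and show Holm as a labelled sensitivity analysis.
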